### 5.2.3.3 Toxicity Management of Infusion Reactions Related to Pembrolizumab

Pembrolizumab may cause severe or life-threatening infusion reactions including severe hypersensitivity or anaphylaxis. Signs and symptoms usually develop during or shortly after drug infusion and generally resolve completely within 24 hours of completion of the infusion. Toxicity management guidelines for pembrolizumab-associated infusion reactions are provided in [Table 7](#).

Table 7 Pembrolizumab Infusion Reaction Treatment Guidelines

NCI CTCAE Grade	Treatment	Premedication at Subsequent Dosing
Grade 1 Mild reaction; infusion interruption not indicated; intervention not indicated	Increase monitoring of vital signs as medically indicated until the participant is deemed medically stable in the opinion of the investigator	None
Grade 2 Requires therapy or infusion interruption but responds promptly to symptomatic treatment (eg, antihistamines, non-steroidal anti-inflammatory drugs [NSAIDs], narcotics, IV fluids); prophylactic medications indicated for $\leq 24$ hours	

Stop infusion

Additional appropriate medical therapy may include, but is not limited to:

IV fluids

Antihistamines

NSAIDs

Acetaminophen

Narcotics

Increase monitoring of vital signs as medically indicated until the participant is deemed medically stable in the opinion of the investigator

If symptoms resolve within 1 hour of stopping drug infusion, the infusion may be restarted at 50% of the original infusion rate (eg, from 100 mL/hr to 50 mL/hr). Otherwise dosing will be held until symptoms resolve and the participant should be premedicated for the next scheduled dose

Participants who develop Grade 2 toxicity despite adequate premedication should be permanently discontinued from further study treatment

	Participant may be premedicated 1.5 hours ( $\pm 30$ minutes) prior to infusion of pembrolizumab with: 

Diphenhydramine 50 mg PO (or equivalent dose of antihistamine)

Acetaminophen 500-1000 mg PO (or equivalent dose of analgesic)

NCI CTCAE Grade	Treatment	Premedication at Subsequent Dosing
Grade 3 or 4 Grade 3: Prolonged (ie, not rapidly responsive to symptomatic medication and/or brief interruption of infusion); recurrence of symptoms following initial improvement; hospitalization indicated for other clinical sequelae (eg, renal impairment, pulmonary infiltrates) Grade 4: Life-threatening; pressor or ventilatory support indicated	

• Stop infusion

• Additional appropriate medical therapy may include, but is not limited to:

• Epinephrine**

• IV fluids

• Antihistamines

• NSAIDs

• Acetaminophen

• Narcotics

• Oxygen

• Pressors

• Corticosteroids

• Increase monitoring of vital signs as medically indicated until the participant is deemed medically stable in the opinion of the investigator

• Hospitalization may be indicated

• **In cases of anaphylaxis, epinephrine should be used immediately

• Participant is permanently discontinued from further study treatment

	No subsequent dosing

Appropriate resuscitation equipment should be available at the bedside and a physician readily available during the period of study treatment administration.  
For further information, please refer to the Common Terminology Criteria for Adverse Events (CTCAE), version 4.0 at <http://ctep.cancer.gov>

### 5.2.4 Replacement of Subjects During DLT Evaluation Period

In order to determine safety, all subjects selected must meet the criteria for evaluability for Cycle 1. Subjects are considered non-evaluable for DLT assessment and will be replaced if:

- They are enrolled but not treated
- They discontinue from the trial prior to completing all the safety evaluations for reasons other than treatment-related adverse events
- They receive less than 90% of the total MK-1248 or pembrolizumab infusion in Cycle 1 ( e.g., because the infusion had to be discontinued due to an infusion reaction) and did not experience a DLT

Non-evaluable subjects will not be counted toward the cohort total for DLT evaluation.

If a subject experiences a DLT in Cycle 1, study treatment may be discontinued following discussion between the sponsor and Investigator. However, if the subject is deriving clinical

benefit from the study treatment, the subject may be allowed to continue after discussion between the sponsor and the Investigator.

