### 5.2.2 Definition of Dose Limiting Toxicity

DLT's will be defined from toxicities observed during the first cycle of treatment (21 days) for each dose level. See Section 5.2.4 for rules on replacement of subjects in the DLT period.

The occurrence of any of the following toxicities during Cycle 1, if assessed by the Investigator to be possibly, probably or definitely related to study drug (MK-1248 in Arm 1 or the MK-1248 with pembrolizumab combination in Arm 2), will be considered a DLT:

1. Grade 4 non-hematological toxicity (not laboratory)
2. Grade 4 hematological toxicity lasting  $\geq 7$  days, except thrombocytopenia
  - a. Grade 4 thrombocytopenia of any duration
  - b. Grade 3 thrombocytopenia is a DLT if associated with bleeding:
3. Any Grade 3 non-hematological toxicity (not laboratory), with the exception of Grade 3 nausea, vomiting or diarrhea, which will not be considered a DLT unless lasting more than 3 days despite optimal supportive care
4. Any Grade 3 or Grade 4 non-hematological laboratory abnormality, if
  - medical intervention is required, or
  - the abnormality leads to hospitalization, or
  - the abnormality persists for  $>1$  week
5. Febrile neutropenia Grade 3 or Grade 4
6. Any drug-related AE which caused subject to discontinue treatment during Cycle 1
7. Grade 5 toxicity
8. Any treatment-related toxicity which causes a greater than 2 week delay in initiation of Cycle 2

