## **5.8 Subject Withdrawal/Discontinuation Criteria**

Subjects may withdraw consent at any time for any reason or be dropped from the trial at the discretion of the investigator should any untoward effect occur. In addition, a subject may be withdrawn by the investigator or the Sponsor if enrollment into the trial is inappropriate, the trial plan is violated, or for administrative and/or other safety reasons. Specific details regarding discontinuation or withdrawal procedures; including specific details regarding withdrawal from Future Biomedical Research, are provided in Section 7.1.4 – Other Procedures.

In this trial, a subject may discontinue from treatment but continue to participate in the regularly scheduled activities, as long as the subject does not withdraw consent. Discontinuation from treatment is permanent. Once a subject has discontinued treatment, even though he/she continues to be monitored in the trial, he/she shall not be allowed to begin treatment again.

Note: Subjects who discontinue treatment for reasons other than PD will have post-treatment follow-up for disease status until PD, initiating a non-study cancer treatment, withdrawing consent, or becoming lost to follow-up.

A subject must be discontinued from the trial for any of the following reasons:

- The subject or legal representative (such as a parent or legal guardian) withdraws consent.
- Confirmed disease progression

A subject must be discontinued from treatment (but may continue to be monitored in the trial) for any of the following reasons:

- The subject withdraws consent for treatment
- Confirmed disease progression
- Unacceptable adverse events (See Dose Modification Section 5.2.3)
- Intercurrent illness that prevents further administration of treatment
- Investigator's decision to withdraw subject
- Subject has confirmed positive serum pregnancy test
- Noncompliance with study treatment or procedure requirements
- Administrative reasons
- Completed treatment as defined in this protocol

[Click here to enter text.](#)

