### 8.5 Analysis Populations

#### 8.5.1 Safety Analysis Populations

The All-Subjects-as-Treated (ASaT) population will be used for the analysis of safety data in this study. The ASaT population consists of all subjects who received at least one dose of study treatment. In case of treatment administration errors, subjects will be analyzed according to the treatment they actually received. However, in the MK-1248 and pembrolizumab combination arm (i.e. Arm 2), if some subjects received only pembrolizumab, but did not receive any dose of MK-1248, these subjects will be included in the ASaT population, but their safety data will be presented separately. For DLT evaluation, ASaT subjects that were observed for safety for 21 days after the first dose of assigned treatment or experienced a DLT prior to 21 days after the first dose of assigned treatment (subjects evaluable for DLT as described in Section 5.2.4) will be used.

At least one laboratory or vital sign measurement obtained subsequent to at least one dose of study treatment is required for inclusion in the analysis of each specific parameter. To assess change from baseline, a baseline measurement is also required.

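### The second replacement criterion in 5.2.4 omits the DLT exception, so 5.2.4 and 8.5.1 give different DLT counts for the same subject

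*Combined protocol and SAP*

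**What the plan says.** Section 5.2.4 opens its list with "Subjects are considered non-evaluable for DLT assessment and will be replaced if" and gives three grounds. The first is enrollment without treatment. The second is "They discontinue from the trial prior to completing all the safety evaluations for reasons other than treatment-related adverse events". The third is receipt of less than 90% of either infusion in Cycle 1, and it is limited by the words "and did not experience a DLT". The section then states: "Non-evaluable subjects will not be counted toward the cohort total for DLT evaluation".

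Section 8.5.1 defines the set used for DLT evaluation as treated subjects who were observed for 21 days "or experienced a DLT prior to 21 days after the first dose of assigned treatment (subjects evaluable for DLT as described in Section 5.2.4". It sets no condition on what happens after the DLT.

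Section 5.9 allows no replacement except under 5.2.4. Sections 8.1 and 8.4.2 name DLT as the primary safety endpoint.

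**The concern.** The second ground turns on why the subject left, not on whether a DLT had already occurred. The third ground, one line below, carries the exception, so the authors knew how to write it. Its absence from the second ground leaves a rule under which an observed DLT can leave the live cohort count, while the analysis section keeps it and names the same rule as its authority.

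The count drives every 3+3 step, every Table 4 action and the DLT rate reported at the RP2D. If two definitions are in force, the count behind a dose decision and the count in the report can differ for the same dose. The difference runs in one direction: the literal 5.2.4 count is never higher than the 8.5.1 count.

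**Working it through.** The plan gives no figure on this point, so there is none to reproduce.

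**Step 1: one subject followed through the text.** Suppose a subject has a Cycle 1 toxicity that meets 5.2.2 and is judged drug-related, then withdraws consent before Day 21 for an unrelated reason.

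- 5.2.4, first ground (not treated): not met.
- 5.2.4, second ground: met. The subject has left the trial early, and the reason is not a treatment-related AE.
- 5.2.4, third ground: not met, and the DLT would block it in any case.
- Result under 5.2.4: non-evaluable, replaced, outside the cohort total.
- Result under 8.5.1: included, because the DLT came before 21 days.
- No other section supplies the missing exception; 5.9 points back to 5.2.4.

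**Step 2: which exits qualify.** A subject who leaves because of the DLT falls outside the second ground by its own wording, and 5.2.2 item 6 already makes this a DLT: "Any drug-related AE which caused subject to discontinue treatment during Cycle 1". Under "A subject must be discontinued from the trial for any of the following reasons", section 5.8 lists withdrawal of consent and confirmed progression. Progression rarely fits: on-study imaging starts at 9 weeks (63 days) and confirmation comes at least 4 weeks later (7.1.2.6, 7.1.2.7.1), against a 21-day window. Consent withdrawal, death from another cause and the occasional administrative withdrawal remain.

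**Step 3: effect of one such subject**, if the replacement has no DLT (rules from 5.2.1.4, 5.2.1.5 and Table 4).

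| DLT kept | Action | DLT dropped | Action |
|---|---|---|---|
| 1/3 | enroll 3 more | 0/3 | escalate |
| 2/6 | stop escalation | 1/6 | escalate |
| 6/14 | D | 5/14 | S, confirmation stops |

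**Step 4: illustration of size.** Let p be the true DLT rate. Let q be the share of subjects with a DLT who then leave under the second ground. The documents do not give q; I take 5% to 20%.

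- Counted rate: p' = p(1-q) / [p(1-q) + (1-p)] = p(1-q) / (1-pq).
- 3+3 escalation probability (0/3, or 1/3 then 0/3): (1-p)^3 + 3p(1-p)^5, evaluated at p'.
- Example, p = 0.30 and q = 0: 0.343 + 0.151 = 0.494.
- Example, p = 0.30 and q = 0.20: p' = 0.24/0.94 = 0.2553, which gives 0.588.

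| p | q | p' | P(escalate) | P(at most 5/14) |
|---|---|---|---|---|
| 0.30 | 0 | 0.300 | 0.49 | 0.78 |
| 0.30 | 5% | 0.289 | 0.52 | 0.81 |
| 0.30 | 10% | 0.278 | 0.54 | 0.83 |
| 0.30 | 20% | 0.255 | 0.59 | 0.88 |
| 0.40 | 0 | 0.400 | 0.31 | 0.49 |
| 0.40 | 5% | 0.388 | 0.33 | 0.52 |
| 0.40 | 10% | 0.375 | 0.35 | 0.56 |
| 0.40 | 20% | 0.348 | 0.40 | 0.65 |

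The last column is a single look at 14 subjects and ignores the earlier Table 4 decisions.

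The table assumes that every subject without a DLT completes Cycle 1. If they left at the same rate q, both definitions would replace them. The literal 5.2.4 count would then estimate p, and the 8.5.1 count would estimate p / [p + (1-p)(1-q)]. At p = 0.30 and q = 10% that is 0.30/0.93 = 0.323, with escalation probability 0.45 against 0.49. The gap between the two definitions is then about 4.5 points (0.494 - 0.449), the same as in the table (0.539 - 0.494). Which count lies nearer the true rate depends on who leaves.

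**The case against.** The best defence has four parts.

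1. **Section 8.5.1 shows the intent.** It equates its own set with the evaluable subjects of 5.2.4, so one definition was probably meant. This stands as evidence of intent. It does not remove the conflict, because cohort decisions are made from 5.2.4, and the cross-reference sends the reader to a rule that gives the other answer.
2. **Loss of the DLT is an inference.** Section 5.2.4 takes the subject out of the cohort total; it does not say that an observed DLT is struck. Section 5.2.2 has no evaluability condition, 5.2.1.5 counts subjects who developed a DLT, and 7.1.2.1 has the sponsor and investigators review each cohort before the next opens. This stands in part: a team could keep the event. But non-evaluable and replaced most directly means dropped, and a rule open to both readings does not fix the count.
3. **Enrollment has closed.** Section 1.0 gives 31-Mar-2017 as the cut-off. This stands in full for future conduct: no new replacement or escalation can follow.
4. **The case is narrow and q is unknown.** This also stands. The subject must leave the trial, not only treatment, within Cycle 1 and for a reason other than a treatment-related AE.

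**Conclusion.** The counting rule in 5.2.4 is wrong as written for a narrow class of subjects and conflicts with 8.5.1. Severity is moderate. The textual conflict does not depend on q. The size does: over the assumed 5-20%, the 3+3 escalation probability rises by about 2 to 9 points at a true rate of either 0.30 or 0.40.

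A reader might go further in three ways that the documents do not support:

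- **That the trial is still being steered to higher doses.** With enrollment closed it cannot be, and nothing in the documents shows that any subject with a DLT was replaced.
- **That the final analysis loses DLTs.** By its own words 8.5.1 keeps them; the doubt comes from its reference to 5.2.4.
- **That the effect is large because many subjects leave after a DLT.** Nothing supports a higher q, and those who leave because of the DLT are already outside the second ground.

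Two questions remain open: which subjects enter the DLT summaries and any RP2D estimate, and whether past cohort decisions used the same count as the analysis will.

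**What to change.** - In 5.2.4, end the second criterion with the words the third already has: "and did not experience a DLT".
- State in 5.2.4 that any subject with a Cycle 1 DLT is evaluable and is not replaced. The section then matches 8.5.1, and one set serves both the cohort decisions and the analysis.
- List all subjects replaced during Cycle 1 and check whether any had a DLT first. If one did, include that DLT in the summaries and record which count the cohort decision used.

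The cost is one clause, one sentence and one listing from data already held. No subjects, visits or data collection are added.

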### **5.2.5 Timing of Dose Administration**

Study treatment may be administered up to 3 days before or 5 days after the scheduled Day 1 of each cycle, beginning in Cycle 3. Cycle 2 Day 1 may be administered up to 5 days after the scheduled day 1. In addition, dosing interruptions are permitted in the case of medical/surgical events or logistical reasons not related to study therapy (e.g., elective surgery, unrelated medical events, subject vacation, and/or holidays). Subjects should be placed back on study therapy within 2 weeks of the scheduled interruption, unless otherwise discussed with the Sponsor. The reason for interruption should be documented in the subject's study record.

In Arm 2, pembrolizumab will be administered first on Day 1 of each cycle, with administration of MK-1248 occurring approximately 30 minutes after completion of the pembrolizumab administration.

Based on preliminary safety information from the ongoing study, the Sponsor recommends that all subjects be prophylactically pre-medicated, 1.5 hours ( $\pm$  30 minutes) before infusion with MK-1248, with the following:

- (1) Dexamethasone, 8 mg intravenously;
- (2) Acetaminophen, 1000 mg orally; and
- (3) Loratadine, 10 mg orally.

### **5.2.6 Trial Blinding/Masking**

This is an open-label trial; therefore, the Sponsor, investigator and subject will know the treatment administered.

## **5.3 Randomization or Treatment Allocation**

Treatment allocation by non-random assignment to Arm 1 or Arm 2 will occur centrally using an IVRS/IWRS. Allocation to a treatment arm will take into consideration whether or not a treatment arm is open to allocation based on minimizing enrollment time, ensuring minimum number of days between each study-wide allocated subject for a given dose, and sequencing Arm 2 relative to the study-wide results of Arm 1.

Note: Enrollment into this study has been prematurely discontinued due to program prioritization and not related to any safety concerns. The cut-off date for enrollment is 31-Mar-2017. Subjects who are ongoing in the study after that date and who do not yet meet established protocol discontinuation criteria, as outlined in Section 5.8, will continue to attend study visits and be followed per protocol. Subjects who are ongoing in the study after that date and who do not yet meet established treatment discontinuation criteria, as outlined in Section 5.8, may continue to receive study treatment per protocol, provided the investigator feels such treatment is in the best interest of the subject.

## 5.4 Stratification

No stratification based on age, sex or other characteristics will be used in this trial.

## 5.5 Concomitant Medications/Vaccinations (Allowed & Prohibited)

### 5.5.1 Acceptable Concomitant Medication

Drugs specifically prohibited in the exclusion criteria are not allowed during the ongoing trial. Listed below are some specific restrictions for concomitant therapy use during the course of the trial. If there is a clinical indication for one of these or other medications specifically prohibited during the trial, discontinuation from trial therapy may be required. The investigator should discuss any questions regarding this with the Sponsor. The final decision on any supportive therapy rests with the investigator and/or the subject's primary physician. However, the decision to continue the subject on trial therapy requires the mutual agreement of the investigator, the Sponsor and the subject. All treatments that the investigator considers necessary for a subject's welfare may be administered at the discretion of the investigator in keeping with the community standards of medical care. All concomitant medication will be recorded on the case report form (CRF) including all prescription, over-the-counter (OTC), herbal supplements, and IV medications and fluids. If changes occur during the trial period, documentation of drug dosage, frequency, route, and date will also be included on the CRF.

Palliative and supportive care is permitted during the course of the trial for underlying medical conditions and management of symptoms. Surgery or radiotherapy for tumor control is not permitted during the study; however, radiotherapy or procedures for symptom management is allowed.

All concomitant medications received within 30 days before the first dose of study treatment through the Safety Follow-up Visit should be recorded. After the Safety Follow-up Visit record all medications taken for SAEs and ECIs as defined in Section 7.2.

### 5.5.2 Prohibited Concomitant Medications

Subjects are prohibited from receiving the following therapies during the Screening, and Treatment Phases of this trial:

- Immunotherapy not specified in this protocol.
- Antineoplastic systemic chemotherapy or biological therapy.
- Investigational agents not specified in this protocol.
- Radiation therapy; radiotherapy for symptom management is allowed.
- Live vaccines within 30 days prior to the first dose of study treatment and while participating in the trial. Examples of live vaccines include, but are not limited to, the following: measles, mumps, rubella, chickenpox, yellow fever, rabies, BCG, and typhoid vaccine. Seasonal influenza vaccines for injection are generally killed virus vaccines and are allowed. However, intranasal influenza vaccines (e.g. FluMist®) are live attenuated vaccines, and are not allowed.

- Glucocorticoids for any purpose other than to modulate symptoms from an event of clinical interest. Chronic systemic replacement doses of steroids are allowed. Inhaled steroids for management of asthma are allowed.

Subjects who, in the assessment by the investigator, require the use of any of the aforementioned treatments for clinical management should be removed from the trial. Subjects may receive other medications that the investigator deems to be medically necessary.

The Exclusion Criteria describes other medications which are prohibited in this trial.

There are no prohibited therapies during the Follow-up visits.

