### **7.1.7 Other Procedures**

#### **7.1.7.1 Withdrawal/Discontinuation**

Subjects who discontinue/withdraw from treatment prior to completion of the treatment regimen should be encouraged to continue to be followed for all remaining study visits.

When a subject discontinues/withdraws from participation in the trial, all applicable activities scheduled for the final trial visit should be performed at the time of discontinuation. Any adverse events which are present at the time of discontinuation/withdrawal should be followed in accordance with the safety requirements outlined in Section 7.2 - Assessing and Recording Adverse Events .

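### Section 5.5.2 removes from the trial a subject who needs a prohibited treatment, while 5.5.1, 5.8 and 7.1.7.1 separate stopping treatment from leaving the trial, so scheduled follow-up may be lost until these sections are reconciled

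*Combined protocol and SAP*

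**What the plan says.** Section 5.5.2 lists what is prohibited during screening and treatment: other immunotherapy, systemic chemotherapy or biological therapy, other investigational agents, radiation not given for symptoms, live vaccines, and most glucocorticoid use. Subjects who in the investigator's judgement "require the use of any of the aforementioned treatments for clinical management should be removed from the trial".

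Section 5.5.1 addresses the same situation. If a prohibited medication is clinically indicated, "discontinuation from trial therapy may be required", and "the decision to continue the subject on trial therapy requires the mutual agreement of the investigator, the Sponsor and the subject".

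Section 5.8 treats the two exits as different events: "a subject may discontinue from treatment but continue to participate in the regularly scheduled activities". Its list headed "A subject must be discontinued from the trial for any of the following reasons" has two entries, withdrawal of consent and confirmed progression. It also has a discretionary route, under which "a subject may be withdrawn by the investigator or the Sponsor if enrollment into the trial is inappropriate, the trial plan is violated".

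Under Section 7.1.7.1, subjects who stop treatment early "should be encouraged to continue to be followed for all remaining study visits". When a subject leaves the trial itself, the final-visit activities are done at that point. Section 7.1.8.3.2 continues imaging every 9 weeks for subjects who stop treatment for a reason other than progression.

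Section 5.2.4 makes subjects non-evaluable for DLT, and replaces them, if "They discontinue from the trial prior to completing all the safety evaluations for reasons other than treatment-related adverse events".

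**The concern.** One trigger has two outcomes at different levels: leaving treatment in one section, leaving the trial in the next. Two sites could handle identical subjects differently and both be following the protocol.

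The difference matters because the need for a prohibited drug may accompany toxicity or worsening disease. Ending trial participation at that moment stops scheduled observation of subjects whose later course is of interest in a first-in-human safety study. In Cycle 1 it can also decide whether a subject belongs to the DLT-evaluable set, which carries the primary endpoint.

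**Working it through.** The plan gives no figure on this point, so the check is a comparison of sections, followed by one piece of algebra on the direction of any bias.

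**1. Same trigger, side by side**

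| Section | Outcome when a prohibited treatment is needed | Level |
|---|---|---|
| 5.5.1 | Therapy may have to stop; continuing is possible by three-way agreement | Treatment |
| 5.5.2 | Subject should be removed | Trial |
| 5.8, mandatory trial exit | Trigger not listed | n/a |
| 5.8, discretionary withdrawal | Allowed, for example if the trial plan is violated | Trial, optional |
| 7.1.7.1 and 7.1.8.3.2 | Follow-up continues after treatment stops | Treatment |

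Only 5.5.2 directs removal from the trial for this trigger. The discretionary clause in 5.8 permits removal but does not direct it.

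**2. What literal removal loses**

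- *Scheduled visits.* Final-visit activities move to the day of removal (7.1.7.1). Remaining treatment-phase visits are lost, as are the visits at 3 and 6 months after last dose in the flow chart, with their PK and anti-drug antibody samples.
- *Imaging.* Sections 7.1.2.6 and 7.1.8.3.2 already end imaging at the start of new anticancer therapy. For prohibited treatments of that kind, 5.5.2 costs no imaging. For a glucocorticoid or a live vaccine, the 9-weekly scans would otherwise have continued and are lost.

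**3. What it does not formally end**

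- The AE window is 30 days from cessation of treatment (7.2).
- The SAE and ECI windows are 90 days from cessation, or 30 days if new anticancer therapy starts (7.2.3.1, 7.2.3.2).
- The Safety Follow-Up Visit is mandatory about 30 days after last dose, or before new antineoplastic treatment if that is earlier (7.1.8.3.1).
- Adverse events present at withdrawal are still followed (7.1.7.1).

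None of these has an exception for removed subjects. The duty to report remains. In doubt is how new events would come to light in someone no longer in the trial.

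**4. Removal in Cycle 1**

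- A DLT has already occurred: the subject is counted (8.5.1).
- A drug-related adverse event stops treatment: this is itself a DLT (5.2.2, item 6), and the 5.2.4 criterion quoted above excludes treatment-related reasons.
- No DLT, and the recorded reason is anything other than a treatment-related adverse event: the subject is non-evaluable under 5.2.4.

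In the third case the sections pull apart. The DLT window is 21 days. Cycle 1 has one dosing day, so a 30-day AE window counted from that dose already outlasts it (30 > 21). Section 8.5.1 asks whether the subject was observed for 21 days, whereas 5.2.4 asks whether the subject left the trial before completing the safety evaluations.

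**5. When this would bias the DLT rate**

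Let p be the true DLT rate, r the fraction removed and replaced before a DLT is seen, and q the DLT risk those subjects would have shown. The rate among retained subjects is (p − r·q)/(1 − r), which differs from p by r(p − q)/(1 − r).

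- If q = p, the difference is zero for every r.
- If q > p, the retained rate is too low; if q < p, too high.

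The documents give neither r nor q. With p at the 30% target and r and q purely assumed:

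| r | q = 0.30 | q = 0.50 | q = 0.70 |
|---|---|---|---|
| 5% | 0.300 | 0.289 | 0.279 |
| 10% | 0.300 | 0.278 | 0.256 |
| 20% | 0.300 | 0.250 | 0.200 |

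For example, (0.30 − 0.10 × 0.50)/0.90 = 0.278. The table shows the condition and the direction. It does not estimate a size for this trial.

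**The case against.** The best reply is that this is a wording slip with little consequence. The reporting windows and the safety visit are tied to treatment, not to trial status. Section 5.5.2 itself closes by saying that no therapy is prohibited during follow-up visits, which fits a move into follow-up rather than an exit. The 30-day SAE limit for subjects who start new anticancer therapy shows that the plan expects to keep collecting data from some of them. Section 5.8 allows discretionary withdrawal in any case. Enrolment closed on 31-Mar-2017.

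Much of this stands, and it rules out four stronger readings that a reader might infer:

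- *Safety follow-up ends at removal.* The windows in 7.2 contain no such exception.
- *Everyone removed in Cycle 1 is replaced.* Treatment-related exits fall outside that 5.2.4 criterion, and a drug-related event that stops treatment is a DLT.
- *AE percentages are biased downward because subjects are swapped out.* The ASaT population in 8.5.1 keeps every dosed subject, including those replaced for DLT purposes.
- *A toxic dose passes 3+3 more easily.* If 20% of subjects carried a 60% DLT risk and 80% a 22.5% risk, the overall rate would be 0.2 × 0.6 + 0.8 × 0.225 = 0.30. Removing the first group would raise the pass probability, (1 − p)³ + 3p(1 − p)⁵, from 0.494 to 0.654. Those inputs are in no document. The scenario also needs the whole high-risk group to leave before any DLT and for reasons not recorded as treatment-related. With enrolment closed there is no escalation left to affect.

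The reply does not remove the conflict. A permissive clause in 5.8 does not cancel a directive in 5.5.2, and the closing sentence of 5.5.2 makes that section harder to reconcile with itself.

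**Conclusion.** The conflict is real and the sections must be reconciled. Its certain effect is limited: on a literal reading of 5.5.2, later scheduled visits are lost, together with 9-weekly imaging in subjects who have not started new anticancer therapy. Detection of new events in the 30-day and 90-day windows becomes uncertain, although the reporting duty continues.

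For the primary endpoint the effect is conditional. It needs a Cycle 1 removal without a DLT, a recorded reason other than a treatment-related adverse event, and a link between removal and DLT risk. The documents give no number of affected subjects and no such link, so no size can be stated.

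The follow-up part still matters for subjects who remain on study, since pembrolizumab in Arm 2 may run for up to 24 months (7.1.8.2). The DLT part now concerns only who is classed as evaluable at analysis. Which treatment rule should apply when a prohibited therapy is needed is not judged here.

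**What to change.** Reconcile 5.5.2 with 5.5.1, 5.8 and 7.1.7.1, leaving the decision on trial treatment to whichever rule the sponsor selects. Two sentences are needed:

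1. In 5.5.2, in place of the removal instruction: *Whatever is decided about trial treatment, a subject who needs a prohibited therapy remains, unless consent is withdrawn, in AE, SAE/ECI and imaging follow-up as scheduled in Sections 7.1.8.3 and 7.2.* The existing end points for imaging and for the reporting windows stay unchanged.
2. In 5.2.4: *DLT evaluability of these subjects follows the 21-day observation rule in Section 8.5.1.*

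The cost is the text change and some follow-up contacts that the protocol already schedules. Sample size and endpoints are unaffected.
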